9.3.2 Pharmacokinetic Statistical Methodology

Dose proportionality among the 5 mg, 30 mg (Day 1), 80 mg and 160 mg dose levels will be assessed using a power model.

The PK parameters C_{max} , $AUC_{0-\infty}$, and AUC_{0-24} will be assessed separately using a power model as follows:

$$\log(PK_i) = \alpha + \beta_i \cdot \log(dose_i) + \varepsilon_i$$

where i represents the i th subject, PK represents a pharmacokinetic parameter (AUC or C_{max}), and ε_i is a residual error term. The dose proportionality will be reported as the estimated ratio of dose-normalized means

$$\hat{R}_{dnm} = \left(\frac{h}{l}\right)^{\hat{\beta}_1 - 1}$$

and its 90% CI, where h and l denote the highest and lowest doses included in the model, respectively. The estimates of β along with its 90% CI, predicted geometric mean, and ratio of dose normalized geometric mean will be reported for each parameter.

The following SAS code will be used:

```
proc mixed data=pk;
  by parameter;
  model lpk = ldose / alpha=0.1 residual ddfm=kr;
  estimate 'xx mg' intercept 1 ldose yy / cl;
  estimate 'zz mg - xx mg' ldose pp / alpha=0.1 cl;
  ods output solutionf=est;
  ods output estimates=estims;
run;
```

The above analysis will be repeated for Japanese and Caucasian subjects separately to examine the effect of the population on dose proportionality.

The PK summary tables and figures will be the responsibility of Eli Lilly and Company.

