9.6.7 Safety and Tolerability Statistical Methodology

The relationship between concentrations of LY3337641 and changes from baseline QTcF (Δ QTcF) will be explored to assess the effect of LY3337641 concentration on the Δ QTcF. A scatter plot of the change from baseline in QTcF versus the concentrations with the fitted lines will also be plotted. A linear mixed-effects model will be fitted with the Δ QTcF as the response, the time-matched concentration as a covariate, population (Japanese/Caucasian) as a fixed effect, the population-by-concentration interaction term, and subject as a random effect. If there is no evidence of a difference between Japanese and Caucasian subjects, population will be removed from the model. The intercept and slope from the model along with their 90% CI will be reported. In addition, prediction intervals using C_{\max} estimated at the highest given dose in the study will be reported together with its 90% prediction intervals.

Example SAS code:

```
proc mixed data=ecg alpha=0.1;  
  class subject race;  
  model change = conc race race*conc / cl solution ddfm=kr;  
  random subject;  
run;
```

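### The example SAS code for the concentration-QTcF model would return 95% limits where SAP 9.6.7 promises 90%, and the SAP 9.3.2 code does not create the slope table it requests

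*SAP*

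**What the plan says.** **Concentration-QTcF model, SAP 9.6.7.** A linear mixed model relates the change from baseline in QTcF to the time-matched concentration. The text states: "The intercept and slope from the model along with their 90% CI will be reported". The code below it is labelled an example and opens with "proc mixed data=ecg alpha=0.1". Its MODEL statement carries `cl`, `solution` and `ddfm=kr`, with no ALPHA= option.

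**Dose proportionality, SAP 9.3.2.** A power model is fitted to C_max and the AUC parameters over 5, 30 (Day 1), 80 and 160 mg. Two intervals are promised at 90%:

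- The ratio of dose-normalised means is to be reported with an interval: "and its 90% CI, where h and l denote the highest and lowest doses included in the model, respectively".
- The slope is covered by the next sentence: "The estimates of β along with its 90% CI, predicted geometric mean, and ratio of dose normalized geometric mean will be reported for each parameter". Here the 90% level is attached to β, while the predicted geometric mean is listed without an interval or a level.

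The code is introduced by "The following SAS code will be used". These lines matter:

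- MODEL: "model lpk = ldose / alpha=0.1 residual ddfm=kr"
- First ESTIMATE: "estimate 'xx mg' intercept 1 ldose yy / cl"
- Second ESTIMATE (difference between two doses): carries both `alpha=0.1` and `cl`
- Output request: "ods output solutionf=est"

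**The concern.** In both sections the text names one confidence level and the code does not carry it through to every result.

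The QTcF case matters more. The value 0.1 is visible on the first line of the code, so someone checking the program could easily take the limits to be 90%. The program would run without error and print limits for the intercept and slope. Protocol 10.3.1.2 leaves the detailed QT analysis to the SAP, and Protocol 5.4 explains that ECGs are assessed intensively because thorough ECG data had not been obtained so far. This model is the only model-based ECG analysis in the SAP. If 95% limits were labelled 90%, the upper limit would be a one-sided 97.5% bound instead of 95%. The slope interval would also exclude zero less readily than stated.

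In 9.3.2 the problem is a missing output. The table meant to hold β and its interval would not exist.

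**Working it through.** **Software rules assumed.** These are standard PROC MIXED behaviour. They are not in the documents, and SAS was not available to run.

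1. ALPHA= on a MODEL or ESTIMATE statement sets the level of that statement's limits. Without it the level is 95%.
2. ALPHA= on the PROC statement governs covariance-parameter limits only.
3. The SolutionF table exists only if MODEL has the SOLUTION option.

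The 9.3.2 code is consistent with rule 1, since it writes alpha=0.1 separately on MODEL and on the second ESTIMATE.

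**Level by line.** The stated figure to reproduce is 90% (alpha 0.10).

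| Quantity | Level in the text | Level from the code | Match |
|---|---|---|---|
| Ratio of dose-normalised means (9.3.2, second ESTIMATE) | 90% | 90% | yes |
| Slope β (9.3.2, SolutionF) | 90% | table not created | no direct output |
| Predicted geometric mean (9.3.2, first ESTIMATE) | none stated | 95% | no promise to break |
| QTcF intercept and slope (9.6.7, MODEL) | 90% | 95% | no |

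**The ratio is delivered, and β follows from it.** The contrast between 160 mg and 5 mg uses pp = ln(160/5) = ln 32 = 3.466. Let its 90% limits be L and U.

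- The ratio is 32^(β−1) = exp(β·pp − pp), so its 90% limits are exp(L − pp) and exp(U − pp).
- The 90% limits for β are L/pp and U/pp.

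This was checked on one simulated data set with the planned numbers on active drug (6, 9, 6 and 6 subjects at 5, 30, 80 and 160 mg). The assumed slope was 1.05 and the assumed CV 30%, for illustration only. The 90% interval for β was 0.927 to 1.063 both directly and by rescaling the contrast. The 90% interval for the ratio was 0.776 to 1.244 by both routes.

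**Size of the difference between 95% and 90% limits.** The ratio of half-widths is t(0.975, df) / t(0.95, df).

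For QTcF, the Kenward-Roger degrees of freedom depend on the data, so a range is shown:

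- df 10: 2.2281 / 1.8125 = 1.229 (22.9% wider)
- df 25: 2.0595 / 1.7081 = 1.206 (20.6% wider)
- df 300: 1.193 (19.3% wider)
- normal limit: 1.192 (19.2% wider)

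For the power model, planned numbers on active drug are 9 in Cohort 1 plus 3 × 6 in the single-dose cohorts = 27. Of these, 6 + 3 × 3 = 15 are Japanese and 3 + 3 × 3 = 12 are Caucasian. With df = n − 2:

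- all subjects, df 25: 1.206
- Japanese, df 13: 2.1604 / 1.7709 = 1.220
- Caucasian, df 10: 1.229

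The power-model ratios apply only to the limits of the predicted geometric mean, on the log scale. The ratio of dose-normalised means is not affected.

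**The case against.** The case for leaving this alone has several parts.

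- **The 9.6.7 code is only an example.** The text beside it states 90% without ambiguity, and a programmer may follow the text. This stands and lowers the severity. The example is still the only place where that model's options are set out, so it should agree with the text.
- **The mismatch can be noticed.** PROC MIXED normally prints the alpha value next to the limits, and a missing output data set would be seen when the 9.3.2 program runs. Table layouts are in a separate shell document that is not available here, so it cannot be shown that a table would be mislabelled. This stands: the claim is that it could happen.
- **Little depends on the level.** The sample size is not based on hypothesis tests (Protocol 10.1, SAP 7). No acceptance range is set for the proportionality ratio or slope, and no threshold for the QTcF slope. No named conclusion would change. This also stands.

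A reader might infer that the dose-proportionality intervals as a whole are at the wrong level. The documents do not support that. The interval for the ratio is correctly requested at 90%, and the interval for β can be recovered exactly from the same contrast. A reader might also count the 95% default on the first ESTIMATE as a broken promise, but the text attaches no level to the predicted geometric mean.

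**Conclusion.** Wrong as written; minor severity.

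- **QTcF model (9.6.7):** the example code would give 95% limits for the intercept and slope against a stated 90%, about 19% to 23% wider. This is the main part of the point.
- **Power model (9.3.2):** the slope table that the code requests is not created, so β and its promised 90% interval are not output directly. This gap is confined to 9.3.2, because the 9.6.7 MODEL statement does have SOLUTION.
- **First ESTIMATE (9.3.2):** its 95% default is out of step with the alpha=0.1 used elsewhere in the same code, and no more than that.

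Point estimates do not change, and any error makes intervals wider, not narrower. The conclusion rests on the PROC MIXED rules listed above. The power-model figures also assume that all planned active subjects contribute. If the 30 mg Day 1 data gave no AUC from zero to infinity, n for that parameter would be 18 (df 16, ratio 1.214), or 9 per population (df 7, ratio 1.248).

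**What to change.** **SAP 9.6.7:** put the level on the MODEL statement, with options `/ cl solution alpha=0.1 ddfm=kr`.

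**SAP 9.3.2:** extend the MODEL options to `/ solution cl alpha=0.1 residual ddfm=kr`, so that SolutionF is created with 90% limits for β. For consistency, add `alpha=0.1` to the first ESTIMATE. If an interval for the predicted geometric mean is to be reported, state its level in the text as well.

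The cost is four option entries: ALPHA= twice, SOLUTION and CL. There is no change to the design, data or models, and no statistical downside. If the SAP is not reissued, the same edits can be made in the analysis programs, with the confidence level checked against the printed alpha before tables are labelled.

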10.3.2.2. Pharmacokinetic Statistical Inference

The dose proportionality of selected LY3337641 PK parameters, including log transformed C_{\max} and relevant AUC values will be examined for all subjects and for each population across the entire dose range using a power model approach (Smith et al. 2000) to estimate the slope of the power model, which represents the ratio of dose-normalized geometric means. Exploratory power model analysis based on the model including race and race-by-dose interaction terms will also be performed to examine the effect of the race on dose proportionality.

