3. INTRODUCTION

This SAP has been developed after review of the Clinical Study Protocol (final version dated 24 December 2016).

This SAP describes the planned analysis of the safety, tolerability, pharmacokinetic (PK) and pharmacodynamic (PD) data from this study. A detailed description of the planned TFLs to be presented in the clinical study report (CSR) is provided in the accompanying TFL shell document.

The intent of this document is to provide guidance for the statistical and PK analyses of data. In general, the analyses are based on information from the protocol, unless they have been modified by agreement between Eli Lilly and Company and Covance Early Clinical (EC) Biometrics. A limited amount of information concerning this study (e.g., objectives, study design) is given to help the reader's interpretation. This SAP must be signed off prior to first subject administration for this study. When the SAP and TFL shells are agreed upon and finalized, they will serve as the template for this study's CSR.

This SAP supersedes the statistical considerations identified in the protocol; where considerations are substantially different, they will be so identified. If additional analyses are required to supplement the planned analyses described in this SAP, they may be performed and will be identified in the CSR. Any substantial deviations from this SAP will be agreed upon between Eli Lilly and Company and Covance EC Biometrics and identified in the CSR. Any minor deviations from the TFLs may not be documented in the CSR.

This SAP is written with consideration of the recommendations outlined in the International Conference on Harmonisation (ICH) E9 Guideline entitled Guidance for Industry: Statistical Principles for Clinical Trials¹ and the ICH E3 Guideline entitled Guidance for Industry: Structure and Content of Clinical Study Reports².

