4.3 Exploratory Objectives

- To explore the PD following single and multiple doses of LY3337641 in healthy Japanese and Caucasian subjects.

- To explore the safety, tolerability, PK, and PD of LY3337641 in Japanese subjects in relation to Caucasian subjects.
- To explore the effect of LY3337641 on ECG findings in healthy Japanese and Caucasian subjects.

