9. STATISTICAL METHODOLOGY

9.1 General

Data listings will be provided for all data that is databased. Summary statistics and statistical analysis will only be presented for data where detailed in this SAP. For continuous data, summary statistics will include the arithmetic mean, arithmetic standard deviation, median, min, max and N; for log-normal data (e.g. the PK parameters: area under the concentration versus time curve [AUC] and maximum observed drug concentration [C_{max}]) the geometric mean and geometric coefficient of variation (CV%) will also be presented. For categorical data, frequency count and percentages will be presented. Data listings will be provided for all subjects up to the point of withdrawal, with any subjects excluded from the relevant population highlighted. Summary statistics and statistical analyses will generally only be performed for subjects included in the relevant analysis population. For the calculation of summary statistics and statistical analysis, unrounded data will be used.

Mean change from baseline is the mean of all individual subjects' change from baseline values. Each individual change from baseline will be calculated by subtracting the individual subject's baseline value from the value at the timepoint. The individual subject's change from baseline values will be used to calculate the mean change from baseline using a SAS procedure such as Proc Univariate.

Data will be also summarized by population (overall, Japanese and Caucasian) where appropriate.

Data analysis will be performed using SAS[®] Version 9.3 or greater.

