11. CHANGES FROM THE PROTOCOL SPECIFIED STATISTICAL ANALYSES

There were no changes from the protocol specified statistical analyses.

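### SAP 9.3.2 drops, without declaring it, the protocol's power model with race and race-by-dose terms, so no direct Japanese–Caucasian contrast is planned for Cmax or AUC

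*SAP*

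**What the plan says.** Protocol 10.3.2.2 sets out two pieces of work on dose proportionality. The first is a power model for Cmax and AUC, fitted to all subjects and within each population. The second comes on top of it: "Exploratory power model analysis based on the model including race and race-by-dose interaction terms will also be performed". Its stated purpose is to examine how race affects dose proportionality.

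SAP 9.3.2 carries over the first piece. Its SAS statement is "model lpk = ldose / alpha=0.1 residual ddfm=kr", so log dose is the only covariate. Race enters only through subsetting: "The above analysis will be repeated for Japanese and Caucasian subjects separately to examine the effect of the population on dose proportionality". The section contains no model with a race or race-by-dose term.

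Three other SAP statements bear on this:
- Section 3: "This SAP supersedes the statistical considerations identified in the protocol; where considerations are substantially different, they will be so identified".
- Section 9.1: "Summary statistics and statistical analysis will only be presented for data where detailed in this SAP".
- Section 11: "There were no changes from the protocol specified statistical analyses".

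Section 4.3 lists among the exploratory objectives: "To explore the safety, tolerability, PK, and PD of LY3337641 in Japanese subjects in relation to Caucasian subjects". Protocol Table JPDB.1 gives Cmax and AUC among the endpoints for that objective.

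**The concern.** The protocol says the joint model will be done as well as the per-race fits. The SAP gives the joint model's purpose to the per-race fits and leaves the model out. Since the SAP overrides the protocol's statistics and limits analysis to what it details, following it means the joint model is not run. Section 11 is then inaccurate on this point.

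The joint model is the only between-race PK analysis to which the protocol commits, and comparing PK between the races is a stated exploratory objective of the first study in Japanese subjects. Without it, the report shows two slopes and two sets of predicted geometric means side by side. The reader must form the contrast and has no planned interval to show how uncertain it is. Two slopes that look alike could then be taken as evidence of no race effect.

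The point is confined to Cmax and AUC. For change in QTcF, SAP 9.6.7 does model race jointly, with "population (Japanese/Caucasian) as a fixed effect, the population-by-concentration interaction term, and subject as a random effect".

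**Working it through.** **Comparing the texts**

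| Analysis of Cmax and AUC | Protocol 10.3.2.2 | SAP 9.3.2 |
|---|---|---|
| Power model, all subjects | yes | yes |
| Power model within each race | yes | yes |
| Joint model with race and race-by-dose | yes, additional | absent |
| Change declared | – | none (section 11) |

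The protocol version does not explain the gap. The SAP cites the version of 24 December 2016, which precedes Amendment (a). The changes listed in protocol Appendix 7 concern the Schedule of Activities, the chest x-ray exemption and the race inclusion criterion; none touches 10.3.2.2.

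**Sample size.** The only planning figure is 36 to 48 completers, and it reproduces: 12 + 3 × 8 = 36 without optional Cohort 5, and 2 × 12 + 3 × 8 = 48 with it. There is no power calculation to reproduce.

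**Inputs for the precision of the omitted contrast**
- Active subjects at 5 / 30 (Day 1) / 80 / 160 mg (SAP 5 and 9.3.2, without Cohort 5): Japanese 3 / 6 / 3 / 3 = 15; Caucasian 3 / 3 / 3 / 3 = 12; total 27.
- Two-sided 90% intervals (SAP 9.3.2).
- Between-subject CV is not in the documents. I assume 25%, 40% and 60%. With σ = √ln(1 + CV²), σ = 0.246, 0.385, 0.555.

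**Slope difference, joint model.** The model is log PK = race + log dose + race × log dose, with 27 − 4 = 23 residual df and t(0.95, 23) = 1.714. The sums of squares of log dose about the race mean are 20.48 (Japanese) and 20.37 (Caucasian). The standard error of the interaction is σ × √(1/20.48 + 1/20.37) = 0.313σ, so the half-width is 1.714 × 0.313 × σ.

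**Slope difference, separate fits.** The two slopes differ by exactly the joint model's interaction coefficient; a simulated data set confirmed this. Combining the two slope standard errors as a root sum of squares, with Welch df of about 22.6, gives the second row below.

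**On the SAP's reporting scale.** R_dnm = (h/l)^(slope − 1), with h/l = 160/5 = 32. The Japanese/Caucasian ratio of R_dnm is therefore known to within a factor of 32^(half-width).

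| Assumed CV | 25% | 40% | 60% |
|---|---|---|---|
| Half-width, joint model | 0.132 | 0.207 | 0.297 |
| Half-width, separate fits (Welch) | 0.132 | 0.207 | 0.298 |
| Factor on ratio of R_dnm | 1.58 | 2.05 | 2.80 |

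**Exposure ratio from the same model.** At dose d the Japanese/Caucasian geometric mean ratio is exp(race + interaction × ln d). Multiply and divide the estimate by these factors for its 90% CI:

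| Dose | CV 25% | CV 40% | CV 60% |
|---|---|---|---|
| 5 mg | 1.36 | 1.62 | 2.01 |
| 30 mg | 1.18 | 1.30 | 1.45 |
| 80 mg | 1.21 | 1.35 | 1.55 |
| 160 mg | 1.29 | 1.49 | 1.77 |
| 1 mg (raw race coefficient) | 1.65 | 2.19 | 3.10 |

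The raw race coefficient is the contrast at ln d = 0, that is 1 mg, below the lowest dose studied.

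**Sensitivity for AUC0-∞.** Protocol 10.3.2.1 names AUC0-∞ for the single-dose cohorts only, and Day 1 sampling in Cohort 1 ends at the 24-hour predose sample. If AUC0-∞ cannot be had at 30 mg, that analysis has 18 subjects and 14 df, and the half-widths become 0.137, 0.214 and 0.307.

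**The case against.** The strongest reply is that little is lost. SAP 9.3.2 keeps the stated purpose and reports each race's slope with a 90% CI. The slope difference can be had by subtraction, and the separate fits are as precise as the joint model. This is correct, and it limits the point: what goes missing is a planned and reported contrast with its interval, not information or precision.

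Second, the protocol promises the effect of race on dose proportionality, not an exposure ratio. That is also right. The dose-specific ratios go beyond the protocol text and are only a suggestion.

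Third, section 3 of the SAP requires only substantial differences to be identified, and replacing an exploratory model with stratified fits might not count as one. Even so, section 11 says flatly that nothing changed, which is inaccurate whatever the threshold. Nothing suggests intent.

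Fourth, both documents allow additional analyses, the sponsor owns the PK tables and figures, and the table shells are a separate document not available here. A general permission or ownership of tables does not plan a specific model. The finding rests on the SAP text, which confines statistical analysis to what it details.

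Finally, the study was not sized for hypothesis tests, so the interval would be wide. That supports reporting it: its main use is to show that similar slopes do not establish similarity.

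**Conclusion.** The concern holds. The SAP omits an analysis to which the protocol commits and states that there were no changes. If the SAP is followed, no between-race estimate or interval for Cmax or AUC is planned, although comparing PK between the races is a stated exploratory objective.

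This should be fixed, but it is not a critical flaw. The analysis is exploratory and no primary or secondary endpoint is affected. The textual finding depends on no assumption. The precision figures depend on the assumed CVs, on full enrolment of Cohorts 1 to 4 without Cohort 5, and on 30 mg Day 1 data being usable for each parameter; losing those data for AUC0-∞ changes the half-widths little.

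**What to change.** 1. Add the protocol's model to SAP 9.3.2: lpk = race ldose race*ldose, with race as a class variable and the SOLUTION and CL options on the MODEL statement, keeping alpha=0.1. Report the slope difference with its 90% CI for Cmax, AUC0-∞ and AUC0-24. Keep the per-race fits.
2. Optionally, and beyond the protocol text, use ESTIMATE statements to report the Japanese/Caucasian geometric mean ratio with 90% CI at 5, 30, 80 and 160 mg. Do not report the raw race coefficient as that ratio.
3. Correct section 11. If the sponsor prefers to leave the joint model out, section 11 should declare this and give the reason.

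The cost is a few lines of SAS and SAP wording, with no new data or visits.

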9.4 Pharmacodynamic Assessment

9.4.1 Pharmacodynamic Analysis

Free Bruton's tyrosine kinase (BTK), total BTK, and BTK occupancy will be listed and summarized by population, treatment, and timepoint using standard descriptive statistics. BTK occupancy will be calculated as follows:

$$\text{BTK occupancy} = \frac{\text{Total BTK} - \text{Free BTK}}{\text{Total BTK}}$$

Change from baseline (Day 1 predose) in BTK occupancy will also be summarized and listed. Furthermore, mean and individual profiles of BTK occupancy will be presented over time.

Additional analysis will be performed if warranted upon review of the data.

